3.2 Investigational Product (treatment) and Indication

Active study medication consists of 7 tablets of fampridine 10mg sustained release (SR) formulated for oral administration (Fampyra®), manufactured by

Alkermes Pharma Ireland Ltd, Monksland,
Athlone, Co.
Westmeath, Ireland

Biogen Idec (Denmark)
Manufacturing ApS, [name], Hillerød,
DK-3400, Denmark

Fampridine is a potassium channel blocker indicated to improve walking in patients with multiple sclerosis. This was demonstrated by an increase in walking speed (Jeffery and Pharr 2010). Fampyra® whose active ingredient is prolonged release 4-aminopyridine (4-AP), is a broad-spectrum voltage-dependent K⁺ channel blocker, which can increase action potential propagation in demyelinated axons (Chwieduk and Keating 2010). The compound, which is lipid soluble, crosses the axon membrane, blocking the exposed K⁺ channels; this decreases K⁺ loss, increases action potentials and conduction, and promotes synaptic and neuromuscular transmission of nerve signals (Chwieduk and Keating 2010). Prolonged release

fampridine is completely absorbed from the gastrointestinal tract and this more slowly than immediate release (IR) fampridine (Fernandez, Berger et al. 2012). This decreases peak plasma concentration by 50%, which consequently reduces dose-related adverse effects. (Fernandez, Berger et al. 2012). SR fampridine should be administered under fasting conditions: administration with food increases peak plasma concentration, leading to increased risk of adverse effects (Weir, Torkin et al. 2013), see also prescribing information of Fampyra® SR. Tablets should only be taken whole; not divided, crushed, chew, or dissolved.

Apparent first-order terminal elimination half-life $t_{1/2}$ of fampridine SR is 5.2 to 6.5 h (Henney, Faust et al. 2011). There will be a wash out period of at least 8 days equalling over 30 half-lives of the active substance fampridine SR ($t_{1/2}=6$ h).

3.3 Preclinical Evidence

In rats, fampridine was found to improve short-term memory performance of old, but not young, animals (Barnes, Eppich et al. 1989).

Further it was found to be able to enhance memory as demonstrated in a 72-h retention of passive avoidance task (Haroutunian, Barnes et al. 1985). The effect of fampridine was also investigated in a mouse model of HIV-1 encephalitis. These mice show impaired spatial memory in radial arm water maze tests. Electrophysiology studies revealed a reduction of long-term potentiation (LTP) in the CA1 region of the hippocampus. Systemic administration of fampridine blocked HIV-1-associated reduction of LTP and improved animal performance in the radial arm water maze (Keblesh, Dou et al. 2009).

3.4 Clinical Evidence to Date

Fampridine was investigated in patients with Alzheimer disease. In one study it partially reversed memory deficits (Wesseling, Agoston et al. 1984). In a second study, results indicated no significant difference in total Alzheimer Disease Assessment Scale Scores (Davidson, Zemishlany et al. 1988).

In patients with Multiple Sclerosis fampridine was investigated in several clinical studies. MS can cause progressive walking impairments, which are improved by Fampridine. Through a blockade of potassium channels, fampridine restores nerve impulse conduction (Tseng, Li et al. 2016), facilitates and enhances synaptic transmission, retards the postsynaptic action potential repolarization (Kasatkina 2016), and increases the release of acetylcholine (Lugaresi 2015).

Fampridine also improves cognitive functions in MS. In a clinical trial MS patients receiving a maximum dose of 0.7 mg/kg of weight per day achieved significantly higher scores in attention span, verbal fluency, planning and graphics and constructive motion (Arreola-Mora, Silva-Pereyra et al. 2019). Another study showed improvement in information processing speed in MS patients receiving 10 mg twice daily for 12 weeks (De Giglio, De Luca et al. 2019). In an earlier study the application of 7.5-52.5 mg of immediate release fampridine over 1-5 days showed motor and visual improvements in MS (Stefoski, Davis et al. 1991).

These findings are consistent with another study, where 40 mg/day led to improvements in attention and concentration in MS patients (Smits et al. 1994). In contrast, no cognitive improvement was reported with a dose of 30–32 mg/day (Rossini et al. 2001; Romani et al. 2004). Considering a long period of administration (9–12 months) at a dose of 20 mg per day, a beneficial effect on both processing speed and working memory has been observed (Pavsic, Pelicon et al. 2015).

3.5 Dose Rationale

The maximum recommended dose of fampridine SR is 10 mg twice daily (approximately 12 hours apart) without food (see prescribing information Fampyra®).

In healthy individuals a single dose of fampridine SR 10 mg achieved a mean maximum plasma concentration (C_{max}) of 21.6 ± 3.89 ng/ mL, with a mean time to maximum plasma concentration (T_{max}) of 3.2 ± 1.5 hours (Smith, Swan et al. 2010). Steady state of fampridine SR will be reached after 5 half-lives of fampridine equalling approx. 30 h (Arzneimittelinformation Swissmedic Fampyra®).

Fampridine is lipid soluble and able to pass the blood–brain barrier (Lemeignan, Millart et al. 1984) and therefore able to reach structures of the prefrontal cortex involved in working memory functions.

Cerebrospinal fluid levels of fampridine peak 30–60 min following peak serum concentration (Donovan, Halter et al. 2000).

Previous studies examining long-term use up to several weeks reported pro-cognitive effects with 10 mg fampridine SR twice daily (see 3.4).

We are interested in the effects on working memory after acute administration of 10 mg fampridine SR as well as in effects after repeated administration of 10 mg fampridine SR twice daily.

We will therefore examine working memory after the first dose of 10 mg fampridine SR (i.e. after a 4 h waiting time to reach maximum plasma concentration)).

Second testing will take place after 3.5 days of twice daily application of 10 mg fampridine SR.

3.6 Explanation for choice of placebo

Placebo is chosen to assess effects of fampridine on memory processes in a cross-over design. Placebo consists of an identically looking tablet manufactured by

Losan Pharma
Losan Pharma GmbH
[name]
[name]
Germany

consisting of additives that are very similar to those used for the verum formulation:

Placebo Tabletten zu Fampyra® 10 mg

Beschreibung:		
Spezifikation:	Bezeichnung Inhaltsstoff:	Menge/Einheit:
Tablettenkern:		
Ph. Eur.	Cellulose mikrokristallin 200	289 mg
Ph. Eur.	Cellulose mikrokristallin 101	122 mg
Ph. Eur.	Hypromellose 6	47 mg
Ph. Eur.	Magnesiumstearat pflanzlich	9,4 mg
Ph. Eur.	Siliciumdioxid hochdispers	2,4 mg
		Summe: 470 mg
Tablettenfilm:		
Ph. Eur.	Hypromellose 6	5,90 mg
Ph. Eur.	Polyethylenglycol	0,90 mg
Ph. Eur.	Titandioxid	1,20 mg
		Summe: 8 mg
		Gesamtsumme: 478 mg

3.7 Risks / Benefits

Fampridine application

Although a short term application of 10 mg fampridine twice daily in healthy participants is generally well tolerated (March and Cardi 2009), participants will be informed of the possible risks associated with taking fampridine. Specific risks that participants need to be aware of are listed below:

- The most frequently occurring AEs included dizziness, headache, insomnia and gastrointestinal discomfort. No discontinuations due to AEs were reported in a study with healthy subjects after administration of a single 10 mg dose (Smith, Swan et al. 2010) as well as after 5 days of twice daily fampridine SR 10 mg in healthy subjects (March and Cardi 2009).
- Fampridine is excreted primarily unchanged in the urine (Blight and Henney 2009). Tolerability and incidence of AEs appear to be dose related, occurring more frequently at plasma concentrations > 100 ng/mL (Van Diemen, Polman et al. 1993). We will therefore exclude subjects with renal impairment to avoid higher plasma levels. To assess renal impairment, we will perform creatinine and uric acid levels in plasma.

- Fampridine is excreted primarily through the organic cation transporter 2 (OCT 2). OCT 2 inhibitors or substrates (e.g. Cimetidine, Carvedilol, Propranolol and Metformin) may inhibit elimination of fampridine and increase the risk of adverse events. Subjects with concomitant use of these drugs are excluded from participation.
- Fampridine can cause seizures. We will exclude people with a history of seizures and subjects at risk of lowered seizure threshold due to e.g. sleep deprivation or alcohol withdrawal after alcohol abuse.
- Despite the fact that fampridine at therapeutic and supratherapeutic doses is not associated with QT prolongation in healthy subjects (March and Cardi 2009) we will exclude subjects with any clinically significant ECG abnormalities or history of cardiovascular disease.
- Fampridine might cause nausea and dizziness and have an additive effect with alcohol. Participants will be advised to avoid alcohol, illegal substances, and any medication (especially psychoactive) due to possible interactions during the course of the study.
- An increased risk of bacterial and viral infections is described in the prescribing information. In a study with 47 healthy subjects receiving 10 mg twice daily doses of fampridine SR over 5 days no viral or bacterial infections were reported (March and Cardi 2009).
- Subjects will be warned about engaging in activities requiring mental alertness, such as driving a car or operating appliances, machinery, etc. Driving a motor vehicle or operating machinery is not allowed during each intervention period of 4 days (96 h) and subjects have to agree to use public transportation or taxi after medication intake for this time period.
- In several in vivo and in vitro studies there was no evidence of drug-related carcinogenicity or mutagenicity (prescribing information Fampyra®).
- Administration of fampridine to animals during pregnancy and lactation resulted in decreased offspring viability and growth at doses 6.8 times the maximum recommended human dose (MRHD) of 20 mg/day. In developmental toxicity studies in rats and rabbits, fampridine was administered orally at doses up to 10 and 5 mg/kg/day, respectively, during the period of organogenesis. These doses are approximately 5 times the MRHD. No evidence of developmental toxicity was found in either species at the highest doses tested, which were maternally toxic. In addition, a case study about a favorable outcome of a pregnancy after exposure with fampridine in the first month of conception is available (Maillart, Gout et al, 2016) For additional safety data, we refer to the prescribing information Fampyra®.

All female of childbearing potential should use adequate contraception starting 10 days before each intervention period and during intervention period, such as an oral, injectable, or implantable contraceptive or contraceptive devices (IUP). To minimize the risk of exposure to IMP we will perform a pregnancy test before administration of study drug on test day 1 and 3.

- All subjects will be informed about possible side effects of medication and advised to inform the investigator about observed side effects due to possible individual differences in metabolism of study medication.

rMT measurement

- Seizures are the most serious possible TMS-related adverse events. Only few cases of TMS induced seizures have been reported so far out of hundreds of thousands examined subjects, and the vast majority of seizures were induced during repetitive TMS (Rossi, Antal et al. 2021). Single-pulse TMS, the method used here, is considered to have no significant risk (Rossi et al., 2009) and studies investigating physiological mechanisms of corticocortical plasticity in healthy subjects, which did not require repeated sessions over several days in order to reach a clinical effect did not show major AE, including seizure occurrence, Thus, there should not be any special concern in studies of this type (Rossi, Antal et al. 2021). We will exclude all persons having experienced a seizure in the past and/or with positive family history (first-degree relatives) of seizures.
- A number of medications have been reported to increase risk of seizure in clinical populations (Stultz, Osburn, et al. 2020) and it was previously assumed that their use in combination with repetitive TMS may confer heightened risk for seizure induction (Rossi et al., 2009). However, empirical evidence for this risk is lacking, and the observed seizure rate even in repetitive TMS patients is extremely low overall despite that the majority of them were on CNS-active medications (Rossi, Antal et al. 2021).

- Risks concerning single pulse rMT measurement in combination with fampridine SR were monitored in MS patients: In recent studies no SAEs during TMS measurements were reported (Marion, Leonid et al 2020), (Ahdab, Shatila et al. 2019), (Krushkov, Shotekov et al. 2006).
- Compared to seizure, syncope is more likely to occur during a TMS investigation, but this is a rare event too. No systematic studies addressed the relative incidence of the two phenomena during TMS, but this is a common experience in many labs (Groppa, 2012). Vasodepressor (neurocardiogenic) syncope is a common reaction to anxiety and physical discomfort and it can take place following TMS, as with many other non-invasive or minimally invasive medical procedures. The cardinal feature that distinguishes syncope from seizure is rapid recovery of full consciousness within few seconds and not minutes (Lin, Ziegler et al. 1982). We will exclude individuals with a history of repeated syncope.

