7 STUDY POPULATION

7.1 Eligibility criteria

Participants fulfilling all of the following inclusion criteria are eligible for the study:

- male or female
- generally healthy
- normotensive (BP between 90/60mmHg and 140/90mmHg)
- BMI between 19 and 29,9 kg/m²
- aged between 18 and 30 years
- fluent German-speaking
- IC as documented by signature
- At least double vaccination against Covid-19

The presence of any one of the following exclusion criteria will lead to exclusion of the participant:

- contraindications to the class of drugs under study, e.g. known hypersensitivity or allergy to 4-aminopyridine
- use of potassium channel blockers within the last 3 months
- concomitant treatment with OCT 2 inhibitors and -substrates (e.g. cimetidine, propranolol)
- acute or chronic psychiatric disorder (e.g. major depression, psychosis, somatoform disorder, suicidal tendency)
- acute cerebrovascular condition
- history of seizures
- risk of lowered seizure threshold (due to e.g. sleep deprivation, withdrawal of alcohol after alcohol abuse)
- renal impairment
- history of malignant cancers
- walking problems (e.g. due to dizziness)
- other clinically significant concomitant disease states (e.g. hepatic dysfunction, cardiovascular disease, diabetes, asthma,
- bradycardia < 50/min during clinical examination
- clinically significant laboratory or ECG abnormality that could be a safety issue in the study
- known or suspected non-compliance (e.g. missing more than one dose of study medication per intervention phase)
- drug or alcohol abuse
- inability to follow the procedures of the study, e.g. due to language or psychological problems of the participant
- participation in another study with an investigational drug within the 30 days preceding and during the present study
- prior participation (less than two years ago) in a study investigating working memory (notably the n-back task)
- enrolment of the investigator, his/her family members, employees and other dependent persons
- smoking (>3 cigarettes per day)
- intake of psychoactive drugs (e.g. benzodiazepines, antidepressants, neuroleptics)
- pregnancy or breast feeding
- experiencing a syncope during basal rMT measuring

Exclusion Criteria concerning TMS measurement

- metal in the brain, skull or elsewhere in the body (e.g., splinters, fragments, clips, etc.)
- implanted neurostimulator (e.g., DBS, epidural/subdural, VNS)
- cardiac pacemaker or intracardiac lines
- medication infusion device

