8.3 Dose

No modifications needed.

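### Minor: the exclusion for renal impairment rests on plasma creatinine and uric acid with no cut-off, although creatinine clearance could be calculated from data already collected

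*Combined protocol and SAP*

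**What the plan says.** Section 3.7 gives the reasoning. The drug's elimination is described as "Fampridine is excreted primarily unchanged in the urine". Adverse events are said to be related to dose, "occurring more frequently at plasma concentrations > 100 ng/mL". The consequence drawn is "We will therefore exclude subjects with renal impairment to avoid higher plasma levels", and the method follows: "To assess renal impairment, we will perform creatinine and uric acid levels in plasma".

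Section 7.1 lists "renal impairment" as an exclusion with no measure or limit. It also excludes "clinically significant laboratory or ECG abnormality that could be a safety issue in the study" and "contraindications to the class of drugs under study, e.g. known hypersensitivity or allergy to 4-aminopyridine". Section 9.4.1 excludes a participant whose laboratory value is both outside the laboratory's range and judged clinically relevant, and it leaves contraindications to the investigator. The same section collects creatinine, height and weight. Age and sex are also known.

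Every participant takes 10 mg twice daily, seven active tablets in all. Section 8.3 on dose reads "No modifications needed". Section 9.3 foresees no laboratory tests after screening, but 9.4.1 repeats the whole screening if the washout exceeds 26 days. Neither creatinine clearance nor an estimated filtration rate is mentioned anywhere.

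**The concern.** The stated aim of the exclusion is to avoid raised plasma levels of a renally excreted drug given at one dose to everyone. The quantity that bears on that aim is absolute clearance. Plasma creatinine is an indirect guide to it, because a small person produces less creatinine and can have an unremarkable value with a fairly low clearance. The laboratory rule in 9.4.1 acts only on out-of-range values, so an in-range creatinine in a light participant prompts nothing. With no limit in 7.1, two investigators could also classify the same participant differently.

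What is at stake is the precision of one safety criterion. The primary comparison is not affected: each participant serves as their own control, and 11.4.2 already examines body weight as a covariate.

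**Working it through.** The plan gives no renal figure to reproduce, so the check asks what clearance an unremarkable creatinine could represent within the eligibility limits.

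**Inputs from the protocol:** age 18-30 and BMI 19-29.9 kg/m² (7.1); mean single-dose peak 21.6 ng/mL, SD 3.89 (3.5); half-life 5.2-6.5 h (3.2); dosing every 12 h.

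**Assumed, not in the documents:** creatinine of 60-90 µmol/L as plausibly in range; heights of 1.50 and 1.60 m; the Cockcroft-Gault formula; for the peaks, drug clearance proportional to creatinine clearance, a reference clearance of 90-120 mL/min and a 70 kg reference weight.

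**Step 1: clearance.** For women, clearance = (140 − age) × kg × 1.04 / creatinine. Weight at BMI 19 is 19 × 1.50² = 42.75 kg or 19 × 1.60² = 48.64 kg.

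| Age, height | 60 µmol/L | 70 | 80 | 90 |
|---|---|---|---|---|
| 30, 1.50 m | 81.5 | 69.9 | 61.1 | 54.3 |
| 30, 1.60 m | 92.7 | 79.5 | 69.6 | 61.8 |
| 18, 1.50 m | 90.4 | 77.5 | 67.8 | 60.3 |
| 18, 1.60 m | 102.9 | 88.2 | 77.1 | 68.6 |

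Lowest: 110 × 42.75 × 1.04 / 90 = 54.3 mL/min. Highest: 122 × 48.64 × 1.04 / 60 = 102.9 mL/min.

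**Step 2: what a limit would do.** Of these 16 values, an assumed limit of 50, 60, 70 or 80 mL/min would exclude 0, 1, 8 or 11. One of the eight, 69.9, crosses 70 if the constant is not rounded (0.85 × 88.4 / 72 = 1.0436). The values form a grid of examples and say nothing about how many participants would be affected.

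**Step 3: peak concentration.** For an average participant the steady-state peak is 21.6 / (1 − 2^(−12/t)), which is 27.1 ng/mL at t = 5.2 h and 29.9 at 6.5 h.

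For an upper bound, take the lowest clearance in the table and stack the unfavourable assumptions: reference 120 mL/min, t = 6.5 h, distribution volume scaled to weight, and a first-dose peak 1.96 SD above the mean.
- First-dose peak: (21.6 + 1.96 × 3.89) × 70 / 42.75 = 47.9 ng/mL.
- Clearance fraction: 54.3 / 120 = 0.453.
- Half-life: 6.5 × (42.75 / 70) / 0.453 = 8.77 h.
- Steady-state peak: 47.9 / (1 − 2^(−12/8.77)) = 78 ng/mL.

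This exceeds every other modelled case and is still below 100 ng/mL. It is probably too high, since the reported SD may already include variation in body size.

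**The case against.** The strongest reply is that the population and the existing rules already cover this. Participants are healthy, aged 18-30 and within BMI limits. History, examination, a broad chemistry panel, the laboratory and contraindication exclusions and the investigator's judgement all apply, and OCT2 inhibitors and substrates are barred. A low Cockcroft-Gault value in a small healthy person may reflect size and not kidney disease, so a clearance limit could act partly as a weight limit. Section 3.7 also attributes excretion mainly to OCT2, so proportionality between drug clearance and creatinine clearance is not established. All of this stands, and it is why the point is minor. It does not answer the narrower observation that none of these rules produces a clearance or says which value counts as impaired.

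A reader might draw three stronger conclusions that the documents do not support.
- *That light participants would have some stated multiple of typical exposure, such as one and a half times.* Such a figure comes from the least favourable corner: age 30, BMI 19, creatinine of 70-90 µmol/L. Against an assumed 100 mL/min, creatinine of 60 µmol/L gives 100 / 92.7 = 1.08 (1.60 m) or 100 / 81.5 = 1.23 (1.50 m) at age 30, and 100 / 102.9 = 0.97 or 100 / 90.4 = 1.11 at age 18.
- *That a wide spread in clearance at one creatinine value reveals missed renal impairment.* At 80 µmol/L and age 30, a woman of 91.6 kg (1.75 m, BMI 29.9) has 130.9 mL/min and one of 42.75 kg has 61.1. The ratio of 2.14 is simply the ratio of the weights.
- *That Section 8.3 prohibits dose changes.* It says only that none are needed.

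**Conclusion.** The point holds as a minor, inexpensive improvement. The protocol gives a pharmacokinetic reason for excluding renal impairment, then names tests that do not yield the relevant quantity and sets no limit. Under the stated assumptions, unremarkable creatinine in light women is compatible with clearances from about 54 to 103 mL/min.

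Nothing stronger is shown. Neither the laboratory's range nor any clearance limit from the prescribing information is in the documents, so no missed case can be demonstrated. A reader might infer toxic exposure from the low end of the range, but the highest modelled peak is 78 ng/mL. There is no bias in the treatment comparison, and no typical exposure multiple should be quoted. The number of participants affected is unknown.

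**What to change.** Keep the present laboratory panel. In 3.7 and 9.4.1, add creatinine clearance by Cockcroft-Gault, in mL/min, at screening and at any repeat screening, using the age, sex, weight and creatinine already collected.

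In 7.1, define renal impairment as a clearance below a pre-specified limit. Use the limit in the current prescribing information if it states one; otherwise the sponsor should set one before enrolment. Retain the existing laboratory and contraindication exclusions and the investigator's judgement alongside it.

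The cost is one derived field in the electronic case report form and changed wording in three sections, with no new sample or visit. The downside is possibly a few more screening failures among small healthy people whose low estimate reflects body size.
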